Nepal being an Asian country is also in the region to have increased cases of cholangiocarcinoma and need rigorous scientific studies to generate evidence to prepare interventions on its prevention and treatment. Cholangiocarcinoma being the major contributing factor for the death of the humans, this needs early diagnosis and treatment system to intrude the increasing mortality and morbidities. Studies should be conducted in its risk factors, disease status, occurrence and other factors so that such studies are considered to estimate the prevention and management of such deadly diseases.

The studies on this sector is in dearth and is in great need of the involvement of academia, medical centers and different institutions. Such studies will provide evidence to plan several interventions for its better and efficient prevention and treatment option.

B.3. Research hypothesis (if applicable):

NA

B.4. Objectives of the research:

General objective (s)

The aim of the study is to assess the clinico-demographic profile of the patient with cholangio-carcinoma undergoing ERCP in Dhulikhel Hospital.

Specific objective(s):

This study holds the objective,

- To identify clinical profile of the patient with cholangio-carcinoma undergoing ERCP
- To describe the demographic profile of the patient with cholangio-carcinoma undergoing ERCP
- To measure the outcome of ERCP procedure in them.
- To identify the association between demographic variable and clinical presentation of the patient with cholangio-carcinoma undergoing ERCP

B.5. Study site and justification:

The study will be conducted in the Endoscopy unit of the Internal medicine department of Dhulikhel Hospital. This hospital has provided services to more than 50 out of 75 districts of the country. It provides services to about 2.7 million people from Kavrepalanchowk, Sindhupalchowk, Dolakha, Lalitpur, Kathmandu, Sindhuli, Ramechhap and other surrounding districts per-year. In Nepal ERCP procedure has been limited to very few Tertiary centers and Dhulikhel Hospital is the pioneer institute to provide the ERCP procedure (since 2011) in the nation. This procedure is mainly performed for the indication of choledocolithiasis, obstructive Jaundice, acute biliary pancreatitis, cholangiocarcinoma, etc. In 2019 only, a total of 1352 patients had undergone ERCP in Dhulikhel Hospital as per the monthly ERCP report book obtained from the Department of Endoscopy of Dhulikhel Hospital.

B6. METHODS/ METHODOLOGY:

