B.6.1 Research Methods (Cross in the appropriate box)

a) Qualitative Research Quantitative Research c) Mixed Research

B.6.2. Study design:

This is a quantitative, retrospective, descriptive cross-sectional observational study.. The outcome and the exposure will be measured at the same time as a snapshot.

B.6.3. Study Variables

The study variables will be the socio-demographic variables and the clinical details of the study participants.

B.6.4. Expected outcomes of the research

The expected outcome of the research is to present a clinical finding of this under studied clinical area in Nepal. Furthermore, this will be a reference for the future researchers to conduct further studies on this sector to enhance the prevention, management and the treatment services.

B.7 STUDY POPULATION AND SAMPLE

B.7.1. Participants/ study population:

Patients with cholangiocarcinoma who had undergone ERCP in Endoscopic Department of Dhulikhel Hospital. The patient's information will be obtained from patients' medical records from the outpatient and inpatient department of Dhulikhel Hospital. Thus, the person will not be contacted directly for the data collection.

B.7.2 Selection criteria:

Inclusion criteria:

- All the participants with cholangiocarcinoma had undergone ERCP
- above 18 years of age.

Exclusion criteria:

- ERCP failed cases

B.7.3. Sampling method/ technique:

We will do purposive sampling from the eligible list obtained from the medical records.

B.7.4. Sampling Unit:

The sampling unit is the patient with cholangiocarcinoma who had undergone ERCP.

B.7.5 Sample size determination:

All the eligible cases listed in the medical record of Dhulikhel Hospital from January 2017 to January 2023. Hospital records showed approximately 75 cases of cholangiocarcinoma per year. So, we will conduct a total population sampling with an estimated sample size of 375.

B.8. Procedure:

First of all, the researcher will get formal approval for data collection in the institution.

- After ethical clearance, data will be collected through a case sheet of the patient and record of ERCP procedure at the department using prepared Per forma.
- Data of procedure outcome will be collected via call to the patient. Before collecting information from the respondent, they will be informed about the objective of the study and will be assured of privacy and volunteering participation.

B.8.1. Data Collection Tools/ Measures:

- Clinical Proforma will be used to collect data

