 - Part I: Socio-Demographic information of patient
 - Part II: Information related to Clinical profile of patient
 - Part III: outcome of ERCP procedure
- The data will then be entered into Microsoft Excel for further data management.

B.8.2. Pretesting

The proforma will be pretested entering about 10 cases so that we can further modify the proforma.

B.8.3. Validity and Reliability of tool

The tool will be the proforma and this will be based on other literatures and as per the experts suggestion. Indeed, the principal investigator is the physician (expert) to perform this procedure in Nepal and other team members have some kind of exposure in this sector.

B.9. Plan for specimen/data management:

(a) Data Processing

- Collected data will be stored in a file to prevent loss or damage.
- Data will be coded and entered in Microsoft Excel Sheet and will be transferred to the Statistical Program for Social Science (SPSS) for further analysis.

(b) Presentation of Data

- Data will be categorized on the basis of research objectives.
- The study will present the descriptive statistics and other details of the variables.

B.10. Plan for data analysis:

B.10. a. SPSS (Statistical Program for Social Science) version 25.0 will be used for descriptive as well as inferential statistics.

B.10. b. Statistical tests: Descriptive statistics (mean, frequency, standard deviation and percentage) will be applied. For inferential statistics, Chi-square test will be used for the analysis of the categorical data while, t-test or correlation will be done for the continuous variables.

B.11. Potential Biases:

There may be some confounders that will direct to the bias of the study. The information in the confounders will be collected and if required will be adjusted in the data analysis.

B.12. Limitations of the study:

- This is not a common disease, so the sample size of the eligible participants is limited.
- The retrospective study nature of this study may not allow us to incorporate as much information as we are seeking. However, future research may address these issues.

B.13. Plan for supervision and monitoring:

- Data will be collected by the co-authors
- Supervision and monitoring will be done by Principal Investigator and the research team

B.14. Plan for dissemination of the research:

The research will be disseminated to:

- Conferences
- Publication in one of the index peer review journal

B.15. DATA AND SPECIMEN BANKING AND/OR SHARING

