B15.1 Management of specimen/data archiving or left-over

NA

B15.2 Specimen/data sharing plan

NA

C. ETHICAL CONSIDERATION

10.1. Ethical issues	Yes/ No	Justification if yes
a. Are human participants included in the study?	Yes	The study aims to determine the clinico-demographic profile of the patients with cholangiocarcinoma undergoing ERCP in Dhulikhel Hospital. But we will not have face to face interaction, as all the information will be obtained from the medical records.
b. Are vulnerable members of the population required for this research? (includes age under 18, pregnant women etc)	No	
c. Are there any risks involved for the participants? If yes, identify clearly what are the expected risks for the human participants in the research and provide a justification for these risks.	No	
d. Are there any benefits involved for the participants? If yes, identify clearly what are the expected benefits for the participants.	No	

C1. SIGNIFICANCE OF THE STUDY

- The study can reveal some risk factors associated with the particular disease i.e Cholangiocarcinoma. Thus, it can be regarded as a baseline study for conducting any intervention.
- It can also be used as a reference for future study purposes in similar types of study.

C2. BALANCE OF RISK AND BENEFIT

C2.1 Risk of the study and Preventive and alleviative measures for risk

C2.1. Risk management:	
Potential risks identified	Proposed measures to mitigate risks
1. No direct risk/harm to the study participants as medical records will be reviewed primarily for patient data collection.	NA
2. Information on the patient's current status will be gathered via telephone interview (only for the feasible cases) where they may have to spare a few minutes for the data, however, this will take only a few minutes.	Verbal consent will be taken and all the information will be provided to the participants if the interaction is required.

C2.3 Benefits of the study

The study will be helpful to the future researcher to base on this and plan further studies so that we can enhance the prevention and treatment processes.

C3. CONSIDERATION FOR VULNERABLE RESEARCH PARTICIPANTS

Check whether your study involves any of the following vulnerable research participants.

- Prisoners
- Pregnant women
- Mentally ill persons
- Cancer or terminally ill patients
- Neonates/infants/children (aged <18)
- HIV/AIDS patients
- Institutionalized persons e.g. military, students, etc.
- Others (please specify).....

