5. EUS FNA

- a) Yes
- b) No

6. If Yes

- 1) Positive
- 2) Negative

7. Brush cytology

- a) Yes
- b) No

8. If Yes

- 1) Positive
- 2) Negative

9. Intra ductal biopsy

a) Yes

b) No

10. If Yes

- 1) Positive
- 2) Negative

11. Surgical operability

- a. Operable
- b. Non-operable
- c. Unknown

12. Lab reports

- a) Total bilirubin.....
- b) Direct bilirubin.....
- c) ALP.....
- d) GGT.....
- e) AST.....
- f) ALT.....
- g) PT.....
- h) INR.....

13. Type of growth

- a. Distal
- b. Hilar

1) Bismuth-I

2) Bismuth-II

3) Bismuth-III

4) Bismuth-IV

5) Bismuth-V

Part 3. Outcome of ERCP procedure

14. Type of stent used in ERCP:

- a) Plastic stent
- b) Metal stent (SEMS)

15. Outcome of Stenting

- a) Immediate
- b) Failed Stenting
- c) Successful stenting

16. Complications

- a) Perforation
- b) Bleeding
- c) PEP
- d) PEC

17. If PEP done

- 1) Within 2 weeks
- 2) After 2 weeks

18. If PEC done

- 1) Within 2 weeks
- 2) After 2 weeks

19. Restenting

- a) Yes
- b) No
- 1) Within 1 month
- 2) Within 2 month
- 3) Within 3 month

20. Radio- Frequency Ablation

- Yes
- No

21. Survival Rate

- a) < 1 month
- b) 3-6 month
- c) 6 month- 1 year
- d) >1 year

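### The protocol contradicts itself on whether ERCP procedure outcomes come from the hospital record or from a telephone call; following the call sentence would expose objective 3 to recall and selection bias

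*Combined protocol and SAP*

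**What the plan says.** Specific objective 3 (B.4) is "To measure the outcome of ERCP procedure in them". B.8.1 divides the proforma into three parts, the last being "Part III: outcome of ERCP procedure". In the appended form that part runs from item 14 to item 21: "Type of stent used in ERCP", "Outcome of Stenting", "16. Complications" (perforation, bleeding, PEP, PEC), the timing of PEP and of PEC, restenting, radio-frequency ablation and survival.

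B.8 gives two sources in consecutive bullets. The first says that "data will be collected through a case sheet of the patient and record of ERCP procedure at the department using prepared Per forma". The second says "Data of procedure outcome will be collected via call to the patient", followed by an assurance about information, privacy and voluntary participation.

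Elsewhere, B.7.1 says that patients will not be contacted directly for data collection. The ethics table (item a), C3 and C4.d name the medical records as the source. The risk table in C2.1 allows a call, but for a narrower purpose: the patient's "current status will be gathered via telephone interview (only for the feasible cases"). C4.a likewise limits the call to a few follow-up matters about patient status.

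**The concern.** The second B.8 bullet is the only sentence that gives procedure outcome a source of its own, and its wording matches both objective 3 and the heading of Part 3. A co-author collecting data could reasonably phone patients for the whole of Part 3. The appended form invites this: it is titled a questionnaire, and its opening instruction addresses a respondent, not a record abstractor.

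Three problems would follow. Technical facts such as stent material, or whether PEP came before or after two weeks, would depend on lay recall. The percentages would cover only patients who could be reached and consented, in a disease whose outcome the Background calls fatal. And a patient who died after a complication could not report it. Meanwhile the ERCP record, which should hold the peri-procedural facts, is already being opened for every case.

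Even if only some collectors read the bullet this way, one percentage could mix record-based and recalled data with nothing on the form to tell them apart.

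**Working it through.** **Step 1. The passages side by side**

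| Place | Source for outcome data |
|---|---|
| B.8, first bullet | Case sheet and ERCP record, on the proforma (which includes Part III) |
| B.8, second bullet | Call to the patient |
| B.7.1 | Records; no direct contact |
| Ethics table (a), C3, C4.d | Records |
| C2.1 row 2, C4.a | Call, for status only; C2.1 adds feasible cases only |

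The statements cannot all hold. B.7.1 and C3 exclude any contact, C2.1 and C4.a allow a limited call, and B.8's second bullet gives the call a wider role. No section assigns a source item by item, names a proxy respondent, or says how patients without an interview are handled.

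**Step 2. Recall interval.** Cases run from January 2017 to January 2023 (B.7.5). The call date is not given. If calls follow the close of the window, the earliest procedures lie at least six years back, while the latest may be recent. Recall quality would therefore vary with calendar year.

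**Step 3. The plan's own number.** The estimated sample size is 375, from about 75 cases a year. 75 × 5 = 375, but the stated window is six years: 75 × 6 = 450. That is a separate discrepancy and this point does not depend on it. I use 375 below.

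**Step 4. Selection, by illustration.** The documents give no complication rate and no share of patients alive, reachable or willing, so all inputs here are assumptions. Let p be the true complication rate and k the chance of interview with a complication relative to without. The rate seen among those interviewed is pk / (pk + 1 − p). With p = 10%:

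- k = 1: 0.10 / 1.00 = 10%, no distortion
- k = 0.75: 0.075 / 0.975 = 7.7%
- k = 0.5: 0.05 / 0.95 = 5.3%

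The result is governed by k, on which the documents are silent. Recall error is not modelled and could run either way.

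**Step 5. Missing data, by illustration.** Let f be the share interviewed and let 10% of them report a complication. The 95% half-width is 1.96 × √(0.1 × 0.9 / n), with n = 375f. The true rate in all 375 can lie anywhere from 0.1f to 0.1f + (1 − f).

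| f | n | Half-width (points) | Bounds on true rate |
|---|---|---|---|
| 100% (record) | 375 | 3.0 | 10% |
| 50% | 188 | 4.3 | 5% to 55% |
| 25% | 94 | 6.1 | 2.5% to 77.5% |
| 10% | 38 | 9.6 | 1% to 91% |

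The first row assumes that the record is complete for every patient. The bounds are worst cases, not expectations. They show how little call-only data could establish about the full series when many patients are not interviewed.

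**The case against.** The strongest reply is that the plan, read as a whole, already takes these data from records. B.8's first bullet fills the whole proforma, Part III included, from the case sheet and ERCP record, and several other sections agree. The second bullet does not mention stent type, stenting result or complications; that link comes from the Part 3 heading. Part 3 also contains restenting and survival, which suit a status call. Entries such as SEMS, PEP and PEC look like chart-abstraction fields, not questions for a patient. The study is descriptive and has no hypothesis, so a loosely worded sentence may seem minor.

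Much of this stands. A reader might infer that the plan has settled on the telephone as the source for objective 3; the documents do not support that. A reader might also infer that only survivors can contribute and that every fatal complication is lost. That requires both call-only collection and no proxy. The survival item has a category below one month, so if calls feed that item, someone other than the patient must be answering. What is missing is a stated proxy rule.

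What the reply does not do is remove the contradiction. The sentence sits in the procedure section that data collectors will follow, and nothing tells them which statement prevails.

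**Conclusion.** The point holds as an unresolved contradiction about the source of the Part 3 data, with a bias that is conditional on B.8's second bullet being followed. In that case the likely direction is under-counting of complications, through non-interview of patients who died or could not be reached.

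A reader might want to attach a percentage to the loss. The documents do not support one: the figures shown under the check run from no distortion to roughly half the true rate, purely according to an assumed relative chance of interview. The effect on the stenting success rate cannot be signed with the same confidence, because recall error has no known direction.

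The conclusion rests on two readings: that procedure outcome in B.8 means Part 3 of the proforma, which the matching wording supports but no sentence states; and that calls are made after January 2023. The contradiction itself needs neither. It should be settled before data collection, because a source that was not recorded is hard to recover afterwards.

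**What to change.** Replace the second B.8 bullet with a rule by item:

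- Items 14-18 and 20 (stent type, stenting result, complications and their timing, ablation) come from the ERCP record and the inpatient or outpatient file, for every included patient.
- The call, to the patient or to a family member if the patient has died, is used for current status and survival, restenting elsewhere, and late complications treated elsewhere.
- Items 16-19 and 21 carry a tick-box for the source, record or call, so that call-added events can be reported separately.
- The denominator is all included patients for items 14-16, patients with PEP for item 17, and patients with PEC for item 18. The number missing is reported for each item.

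Then reconcile B.7.1, the ethics table, C3 and C4.d with this limited call. C2.1 and C4.a already describe a status call and need only the added purposes and the family respondent, whose verbal consent should also be covered.

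The cost is a few sentences and one tick-box. The record is already a data source, so reading these items from it needs no new source. The remaining weakness is that late complications treated at another hospital stay under-recorded for patients for whom no one can be reached; this belongs in the limitations (B.12).

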PART 1: SOCIO-DEMOGRAPHIC CHARACTERISTICS

1. Age (in completed years).....

2. Gender:

Male Female Others (specify).....

3. Ethnicity

- a. Brahmin/chhetri
- b. Newar
- c. Mongolian
- d. Dalit
- e. Terai region
- f.

4. Occupation

- a. Agriculture
- b. Service
- c. Labor
- d. House maker
- e. Student

5. Food habit

- a. Vegetarian
- b. Non-Vegetarian

6. Smoking Habit

- a. Yes
- b. No

7. Alcohol Intake

- a. Non-alcoholic
- b. Moderate
- c. Significant

Part 2: Information related to Clinical profile of the patient

1. Mode of presentation

- a. Cholangitis
- b. Obstructive Jaundice
- c. Non-icteric Cholestasis

2. Comorbidity

- a. Yes
- b. No

3. Symptoms

- a. Itching
- b. Abdominal Pain
- c. Asymptomatic Jaundice
- d. Anorexia
- e. Weight loss

4. Investigations

- a. USG
- b. CT Scan
- c. MRI
- d. MRCP
- e. EUS

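### B.10.b names only mean and SD for the laboratory values: add median, interquartile range and rank-based methods, and state in item 12 which value is taken

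*Combined protocol and SAP*

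**What the plan says.** Section B.10.b gives one rule for all variables. For description: "Descriptive statistics (mean, frequency, standard deviation and percentage) will be applied". For inference, a chi-square test covers categorical data and "t-test or correlation will be done for the continuous variables". The type of correlation is not named. No median, interquartile range, range, transformation, normality check or rank-based test appears anywhere in the document. Section B.9(b) adds "The study will present the descriptive statistics and other details of the variables", which names no further statistic.

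The rule does not single out the laboratory tests, but it applies mainly to them. The open numeric fields on the proforma are age (Part 1) and item 12 of Part 2: total and direct bilirubin, ALP, GGT, AST, ALT, PT and INR. Restenting and survival are recorded in bands. Item 12 asks for each value without a date and without reference to the ERCP.

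Part 2, item 1 offers both "Obstructive Jaundice" and "Non-icteric Cholestasis" as modes of presentation. The fourth specific objective in B.4 is "To identify the association between demographic variable and clinical presentation of the patient with cholangio-carcinoma undergoing ERCP".

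**The concern.** Mean and SD describe a roughly symmetric variable well. The item 12 tests are bounded at zero, and bilirubin in particular may run from near normal in a patient without jaundice to very high in an obstructed one. With a long right tail, or with two clusters, the mean sits above most patients, and mean minus one or two SDs can be negative, which is impossible for these tests.

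The laboratory profile is the main numeric part of the first specific objective, and section C1 offers the study as a baseline for later work. A misleading typical value would therefore be carried forward. Comparisons of means and product-moment correlations are also sensitive to a few extreme values.

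A second, smaller gap concerns timing. A patient with several test results could contribute a value from before or after stenting, and no choice of summary statistic repairs that mixture.

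**Working it through.** **Inputs.** From the plan: the statistics in B.10.b, the fields in item 12, the two presentation categories, and the estimated 375 patients in B.7.5. The plan gives no laboratory distribution, alpha, power or effect size, so there is no planned figure to reproduce on this point. (The 375 equals 75 × 5, while the record window of about six years gives 75 × 6 = 450. That is a separate matter and changes little here.) Assumed: the distributions below and a two-sided 5% level.

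**Step 1: one log-normal population with log-scale SD s.** Mean/median = exp(s²/2), share of patients below the mean = Φ(s/2), SD/mean = √(exp(s²) − 1).

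| s | mean/median | share below mean | SD/mean |
|---|---|---|---|
| 0.3 | 1.05 | 56% | 0.31 |
| 0.5 | 1.13 | 60% | 0.53 |
| 0.7 | 1.28 | 64% | 0.80 |
| 1.0 | 1.65 | 69% | 1.31 |
| 1.2 | 2.05 | 73% | 1.79 |

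Mean minus 2 SD is negative once SD/mean exceeds 0.5, which is from s of about 0.5. Mean minus 1 SD is negative once s exceeds √(ln 2) = 0.83.

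**Step 2: a mixture of non-icteric and obstructed patients.** A share q is non-icteric (median 1 unit, log-SD 0.4) and the rest are obstructed (median 12 units, log-SD τ). Mean = q·exp(0.4²/2) + (1 − q)·12·exp(τ²/2). Medians were found numerically.
- τ = 0.6, q = 10%: mean 0.1 × 1.083 + 0.9 × 12 × 1.197 = 13.04, median 11.04, ratio 1.18.
- τ = 0.6, q = 40%: mean 0.4 × 1.083 + 0.6 × 12 × 1.197 = 9.05, median 6.71, ratio 1.35. The SD is 9.8, so mean minus 1 SD is 9.05 − 9.8 = −0.75.
- Over τ = 0.5 and 0.7 and q = 10% to 40%, the ratio runs from 1.08 to 1.58.

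**Step 3: power, one log-normal population.** Groups of 187 and 188. The log-scale difference is set at s × (1.960 + 0.842) × √(1/187 + 1/188), so that a log-scale t-test has 80% power. At s = 0.8 this is 0.8 × 2.802 × 0.1033 = 0.23, a ratio of 1.26. Simulated power (4,000 runs) of the untransformed t-test is 78, 74, 67, 58 and 52% at s = 0.3, 0.5, 0.8, 1.0 and 1.2. Mann-Whitney stays at about 78%. Type I error of the untransformed t-test, over all group sizes tried, is 4 to 6%.

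**Step 4: power, mixture.** Same group sizes, a 1.3-fold shift in all patients, 2,000 runs:

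| τ | q | t-test, untransformed | t-test, log | Mann-Whitney |
|---|---|---|---|---|
| 0.5 | 10% | 98% | 82% | 98% |
| 0.5 | 20% | 92% | 63% | 91% |
| 0.5 | 40% | 72% | 48% | 77% |
| 0.7 | 10% | 83% | 72% | 84% |
| 0.7 | 20% | 73% | 58% | 70% |
| 0.7 | 40% | 55% | 45% | 60% |

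Here the log-scale t-test is the weakest in all six settings. Mann-Whitney lies between 3 points below and 5 points above the untransformed t-test. If only obstructed patients shift and q = 40%, Mann-Whitney also falls behind: 41% v 69% at τ = 0.5 and 24% v 51% at τ = 0.7.

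**The case against.** The strongest reply is that this is a descriptive study with no hypothesis (B.3) and no power target, so little turns on test efficiency. The fourth objective concerns clinical presentation. Mode of presentation and symptoms are categorical on the form, so chi-square would apply, and nothing says that laboratory values are an endpoint for that objective. At this sample size the t-test keeps its false-positive rate. All of this stands, and it confines the point mainly to description.

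A reader might also infer more than the documents support:
- **That the cohort is mixed by design, so bilirubin must be heavily skewed.** The non-icteric category is one tick-box. Its frequency is not given, and B.7.2 does not require a mix.
- **That the plan prescribes untransformed analysis and only product-moment correlation.** That is read from silence. The correlation could be rank-based, and B.9(b) leaves room for further detail, although it names none.
- **That the planned t-test loses power in general and a log transformation would restore it.** Step 3 shows a loss under one log-normal population. Step 4 shows the reverse for the log-scale test when the two presentations are mixed, which is the very reason for expecting uneven values.

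The timing of item 12 is a data-definition question and lends no support to the point about mean and SD. It is included because the same fields are affected.

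None of this defends naming mean and SD alone for eight zero-bounded tests.

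**Conclusion.** The point holds as a modest, nearly free improvement to the description of the laboratory values. B.10.b names no summary that stays representative if those values are skewed or bimodal. The size rests on assumed distributions: the mean overstates the median by about 5% at log-SD 0.3, by about 30% at 0.7, about twofold at 1.2, and by about 10 to 60% in the illustrative mixtures. The eight tests need not behave alike, and PT and INR may be little affected.

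The documents do not support a claim of false-positive harm or of a general loss of power. Type I error stays near 5%, and whether a rank-based test gains or loses power depends on the distribution and on which patients differ. The reason to name rank-based methods now is that they resist extreme values, match the median as the reported summary, and are fixed before the data are seen.

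The missing time point in item 12 is a sound secondary point. Its size cannot be judged from the documents.

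**What to change.** In B.10.b, state that bilirubin (total and direct), ALP, GGT, AST, ALT, PT and INR are reported as median and interquartile range. Mean and SD may be kept alongside, and for age. State that groups are compared on these tests by Mann-Whitney (two groups) or Kruskal-Wallis (more than two), and that correlations are Spearman. Do not prescribe a log transformation for all tests.

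In item 12, instruct the abstractor to record the last value before the index ERCP, so that values before and after stenting are not mixed. B.8.2 already foresees changes to the proforma after a pretest on about 10 cases, so this can be made there.

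Cost: SAP wording and one abstraction instruction, with the same fields and the same SPSS software. Comparisons are stated as ranks rather than mean differences, and in some mixtures (step 4) the rank test is less powerful than the t-test.

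### C1 promises risk factors for cholangiocarcinoma from a cases-only study, and B.12 does not warn of it; as a minor gap, B.10.b names no test for age across three modes of presentation

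*Combined protocol and SAP*

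**What the plan says.** C1 (Significance of the study) states: "The study can reveal some risk factors associated with the particular disease i.e Cholangiocarcinoma". It then draws an inference: "Thus, it can be regarded as a baseline study for conducting any intervention".

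Three parts of B.7 define who is studied:

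- B.7.1: "Patients with cholangiocarcinoma who had undergone ERCP in Endoscopic Department of Dhulikhel Hospital"
- B.7.2, inclusion: "All the participants with cholangiocarcinoma had undergone ERCP"
- B.7.4: "The sampling unit is the patient with cholangiocarcinoma who had undergone ERCP"

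B.12 gives two limitations: "This is not a common disease, so the sample size of the eligible participants is limited" and "The retrospective study nature of this study may not allow us to incorporate as much information as we are seeking".

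For inferential statistics B.10.b says: "Chi-square test will be used for the analysis of the categorical data while, t-test or correlation will be done for the continuous variables". The fourth specific objective in B.4 is an association between demographic variables and clinical presentation, within the same patients. The proforma records age in completed years (Part 1, item 1) and mode of presentation as one of three unordered categories (Part 2, item 1).

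**The concern.** **Main point.** To call something a risk factor for a disease, one must compare how often it occurs in people with and without that disease. Here everyone has it. A reader who takes C1 at face value could present a common exposure among cases as a risk factor and plan an intervention around it, although the same data would fit harm, no effect or protection. The limitations section gives no warning.

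**Minor point.** Age is the only continuous demographic item. To relate it to mode of presentation with the named tests, the analyst has two options. One is to cut age into bands for a chi-square test, which loses information and leaves the cut-points open until the data are seen. The other is to run several t-tests, which the plan does not state and which raises the chance of a false positive.

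**Working it through.** **Sample size used.** B.7.5 states 375. At 75 cases per year this is 75 × 5 = 375, whereas January 2017 to January 2023 is about six years, and 75 × 6 = 450. The main point does not depend on either figure. The calculations for the minor point use both.

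**Main point: what the design can identify.**

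1. B.7.1, B.7.2 and B.7.4 all make cholangiocarcinoma a condition of entry, so disease status does not vary in the sample.
2. No control group, disease-free ERCP group or external reference rate appears in the document.
3. The odds ratio for an exposure is [p₁/(1 − p₁)] / [p₀/(1 − p₀)], where p₁ is the share exposed among cases and p₀ the share in the source population. The study estimates p₁ and has no information on p₀.
4. Illustration with assumed shares. Suppose 35% of cases smoke (131 of 375; Wilson 95% CI 30.3–39.9%):
   - p₀ = 25%: (0.35/0.65)/(0.25/0.75) = 1.62
   - p₀ = 35%: (0.35/0.65)/(0.35/0.65) = 1.00
   - p₀ = 45%: (0.35/0.65)/(0.45/0.55) = 0.66
5. The interval describes precision among cases only. A larger sample would narrow it and leave the odds ratio just as undetermined.
6. B.11 mentions adjusting for confounders. Adjustment cannot supply a missing comparison group.

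**Minor point: age by mode of presentation.** A t-test compares two groups, and correlation needs two numeric or ordered variables. Neither gives one test across three unordered groups. Chi-square would need age bands, and none are defined. B.9 says data will be categorised by objective, but that concerns presentation and sets no cut-points.

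The consequences were simulated under stated assumptions: age normal with SD 12 years, rounded to whole years; a two-sided 5% level (the plan states none); and assumed group splits.

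*No true difference* (mean 60 in every group, 20,000 datasets per setting):

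| Group sizes | Any of three pairwise t-tests significant |
|---|---|
| 125/125/125 | 12.5% |
| 225/112/38 | 11.6% |
| 300/56/19 | 11.7% |
| 150/150/150 | 12.2% |
| 270/135/45 | 11.7% |
| 360/67/23 | 11.6% |

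One-way ANOVA in the same datasets gave 4.8–5.1%. Chi-square with cuts fixed in advance (at 60; 50 and 70; 60 and 75; or 50, 60 and 70) gave 4.6–5.1%. Taking the best of those four bandings after the fact gave 11.8–12.5%.

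*True difference of 5 years between the extreme means* (10,000 datasets per setting). Each cell is the power of ANOVA against the range over the four fixed bandings:

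| Group sizes | Means 60/60/65 | Means 60/62.5/65 |
|---|---|---|
| 125/125/125 | 93.2% v 75.5–78.2% | 83.8% v 60.0–64.1% |
| 225/112/38 | 57.3% v 33.1–40.5% | 67.5% v 40.3–47.6% |
| 300/56/19 | 32.2% v 17.2–24.1% | 48.2% v 25.7–35.1% |
| 150/150/150 | 97.1% v 83.9–86.5% | 90.7% v 70.8–73.0% |
| 270/135/45 | 64.8% v 37.8–46.3% | 75.7% v 48.8–55.2% |
| 360/67/23 | 39.6% v 20.6–29.4% | 56.2% v 31.3–40.2% |

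ANOVA has the higher power in every cell.

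**The case against.** The best defence is that C1 is one hedged sentence in a significance statement and that nothing operative depends on it. B.3 gives no hypothesis, none of the B.4 objectives seeks causes of the disease, B.6.2 calls the design descriptive, and B.10 plans no exposure–disease estimate. All of this is correct, and it is why the point concerns what may be concluded and leaves the objectives and existing tests alone. It does not remove the claim, because C1 rests its inference to intervention on it.

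The sentence could also be read more mildly, as showing which established risk factors occur among this hospital's cases. The design can support that reading, but it is not what the text says. If it is what was meant, rewording costs nothing.

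On the tests, clinical presentation is broader than the three-category item. Age by a symptom present or absent suits a t-test, age by bilirubin suits correlation, and the categorical demographic items suit chi-square. Only age against an item with more than two categories is left without a test. The study also states no alpha and implies many unadjusted tests, so correcting one pairing does not control error overall. This stands and keeps the second point minor. So does the observation that the power figures depend heavily on assumed splits and means. The direction of the comparison does not change across those settings.

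**Conclusion.** Both points hold.

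The main one is an over-claim in C1 that B.12 leaves unqualified. With cases only, no association with having cholangiocarcinoma can be estimated, at any sample size. That conclusion follows from the selection criteria and needs no assumption; the smoking shares only illustrate it. It should be corrected, but it does not undermine the descriptive objectives or the within-case comparisons of Objective 4.

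The second is a small omission in B.10.b. At an assumed 5% level, filling the gap with unadjusted pairwise t-tests would give 11.6–12.5% false positives against 4.8–5.1% for one ANOVA. Banding age in advance keeps the error rate but costs power: at 375 patients in equal groups, 60–78% against 84–93%. The power figures rest on the assumed SD of 12 years, the 5-year difference and the group splits.

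**What to change.** 1. **C1:** replace the risk-factor sentence with one about the frequency of known risk factors among patients with cholangiocarcinoma undergoing ERCP. Limit it to factors actually recorded. Of those named in A.8, the proforma has separate items only for smoking and alcohol; comorbidity is a single yes/no item.
2. **B.12:** add that there is no comparison group, so associations with having the disease cannot be estimated.
3. **B.10.b:** name one-way ANOVA, or Kruskal-Wallis if the variable is skewed, for a continuous variable across more than two groups, and say in advance how skewness will be judged so that the choice is not left to the results. Keep chi-square for categorical pairs and the t-test for two groups.

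These are wording changes, with no new data and the same SPSS package. The costs are a more modest statement of significance and, for the third change, a global test that does not say which of the three groups differ.
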